Research question and objectives	
DAA-PASS is designed to investigate the question: does DAA therapy for chronic HCV infection increase the risk of early HCC recurrence among a well-characterized group of patients who have received successful HCC treatment interventions, relative to no DAA therapy?
 
The primary objective is to estimate the risk of early HCC recurrence (within the follow up period after the first HCC-free image) associated with DAA therapy exposure relative to no DAA therapy exposure during routine clinical care of HCV-infected patients with successfully treated HCC, in the prospective DAA-PASS cohort.
 
The secondary objectives are to:
 
A. Compare the adjusted incidence of early HCC recurrence (within the follow up period after the first HCC-free image) associated with DAA therapy exposure relative to no DAA therapy exposure during routine clinical care of HCV-infected patients with successfully treated HCC, in the prospective DAA-PASS cohort.B. Estimate the risk of early HCC recurrence (within the follow up period after the first HCC-free image) associated with DAA therapy exposure relative to no DAA therapy exposure including a historical cohort of HCV patients not exposed to DAA with initial HCC diagnosis and subsequent successful treatment of HCC.C. Compare the adjusted incidence of early HCC recurrence (within the follow up period after the first HCC-free image) associated with DAA therapy exposure relative to no DAA therapy exposure including a historical cohort of HCV patients not exposed to DAA with initial HCC diagnosis and subsequent successful treatment of HCC. 
The exploratory objective is to describe in a non-comparative summary the cumulative risk of HCC recurrence over time for the historical cohort alone.

Country(-ies) of study	Will include: United States, France, Germany, Italy, and Spain
Author	TARGET PharmaSolutions, Inc. [name] Contact: [name], RAC Senior Director Scientific and Medical Affairs

Marketing authorisation holder(s)

Marketing authorisation holder(s)	Joint DAA-PASS MAHs (refer to Annex 3 for full list)
MAH contact person	[name], MSci Director, International Regulatory Affairs Gilead Science International [name] [contact] [contact] E-mail: [contact]

2. LIST OF ABBREVIATIONS

AASLD	American Association for the Study of Liver Diseases
AE	Adverse event
AESI	Adverse event of special interest
AFP	Alpha-fetoprotein
ANRS	Agence Nationale de Recherche sur le Sida et les hépatites virales
ADR	Adverse drug reaction
ATC	Anatomical Therapeutic Chemical classification system
AUDIT	Alcohol Use Disorders and Identification Test
BCLC	Barcelona Clinic Liver Cancer
CI	Confidence Interval
CT	Computed tomography
DAA	Direct-acting antiviral
DAA-PASS	A Post-Authorisation Safety Study of Early Recurrence of Hepatocellular Carcinoma in HCV-Infected Patients after Direct-Acting Antiviral Therapy
DMP	Data management plan
EASL	European Association for the Study of the Liver
EC	Ethics Committee
EEIG	European Economic Interest Grouping
ENCePP	European Network of Centres for Pharmacoepidemiology and Pharmacovigilance
EMA	European Medicines Agency
EORTC	European Organization for Research and Treatment of Cancer
EU	European Union
FDA	Food and Drug Administration
GVP	Good Pharmacovigilance Practice
HBV	Hepatitis B virus
HCC	Hepatocellular carcinoma
HCV	Hepatitis C virus
HR	Hazard ratio
ICF	Informed consent form
ICH	International conference on harmonization
ICSR	Individual case safety report
IFN	Interferon
IPCW	Inverse-probability of censoring weighted averages
IRB	Institutional review board
ITA.LI.CA	Italian Liver Cancer Group
MAH	Marketing Authorisation Holder
MedDRA	Medical Dictionary for Regulatory Activities
MELD	Model for End Stage Liver Disease
MRI	Magnetic resonance imaging
PASS	Post-authorisation Safety Study
PRAC	Pharmacovigilance Risk Assessment Committee

Q	Quarter
RFA	Radiofrequency ablation
SAE	Serious adverse event
SAP	Statistical analysis plan
SOC	System Organ Class
SVR	Sustained virological response
TACE	Transcatheter arterial chemoembolization
TARGET-HCC	A 5-year Longitudinal Observational Study of the Natural History and Management of Patients with Hepatocellular Carcinoma; Clinicaltrials.gov Identifier: NCT02954094
TPS	TARGET PharmaSolutions, Inc.
US	United States
WHO	World Health Organization

4. ABSTRACT

4.1. Title

DAA-PASS: A post-authorisation safety study of early recurrence of hepatocellular carcinoma in HCV-infected patients after direct-acting antiviral therapy (DAA-PASS Final Draft Version 3.3, dated 06 Jun 2018).

Sponsored and authored by TARGET PharmaSolutions, Inc. (TPS) and conducted on behalf of the Joint DAA-PASS Marketing Authorisation Holders (MAHs).

4.2. Rationale and Background

Recent reports of direct-acting antiviral (DAA) therapy use for chronic hepatitis C after successful treatment of hepatocellular carcinoma (HCC) have raised concerns that DAA therapy is associated with an increased risk of early HCC recurrence. In contrast, other recently reported studies have indicated no increased risk of early HCC recurrence.

As a response to the initial reports, the European Commission, under Article 20 of Regulation No 726/2004, requested a review of DAAs for the treatment of chronic hepatitis C to evaluate the risk of HCC recurrence. The review was carried out by the European Medicines Agency's (EMA) Pharmacovigilance Risk Assessment Committee (PRAC) and the recommendation was that the DAA MAHs should perform a prospective study to assess the risk of early recurrence of previously treated HCC after DAA therapy for HCV.

Due to the differences in reported results from published studies, the small numbers of patients analyzed, as well as the significant differences in the patient populations and designs in these studies, including differences in methodologies and lack of comparator groups, uncertainty remains about the risk of early HCC recurrence in patients exposed to DAAs relative to those not exposed. Therefore, a larger, controlled study was designed to address these concerns.

As was noted by the PRAC in the 30 Nov 2017 Final Assessment Report as part of the initial assessment of the protocol (EMA procedure: EMEA/H/C/PSP/J/0056.2), a depletion of the

patient pool was identified early as a significant risk for this study. With the current widespread availability and increasing utilization of DAAs within the 5 countries with active DAA-PASS sites as well as worldwide, the population of patients who are naïve to DAA treatment for HCV prior to HCC treatment has dramatically diminished compared to the original enrollment projections provided in the original DAA-PASS protocol.

Although investigators continue to indicate that the population of patients who meet entry criteria is increasingly difficult to find, a number of actions were taken to attempt to increase enrollment. In April 2019 a site survey was conducted, in part, to better understand enrollment challenges. Sites reiterated that patients with HCC and HCV most often present for HCC treatment after having already been treated with a DAA, and as current practice guidelines generally recommend routine screening for patients with HCC risk factors, the likelihood of HCV being undiagnosed and untreated in HCC patients is very low.

Additional steps taken to address the low enrollment rate include the following: 1) creation of a DAA-PASS Advisory Committee; 2) customized site engagement and enrollment plans and enrollment mediation activities; 3) site re-education and motivational visits; 4) identification of potential additional sites willing to consider participation within active countries; 5) conduct of a DAA-PASS Investigator meeting; and 6) revision to the Informed Consent Form to minimize time burden on site staff and study participants.

Although implementation of these enrollment remediation efforts was initiated in 2019, overall the monthly screening and enrollment rates have decreased or have remained unchanged over the course of the year, likely reflecting the lack of the available eligible patient population. Thus, revisions to the current protocol reflect that of a convenience sample.

Since the population of HCC treated patients who have not been treated with DAAs for HCV has decreased dramatically, so as to make the original sample size needed for this study unobtainable, greater reliance on currently available and retrospective data is required. Fortunately, many manuscripts with such data have been published since the start of DAA-PASS.

4.3. Research Question and Objectives

DAA-PASS is designed to investigate the question: does DAA therapy for chronic HCV infection increase the risk of early HCC recurrence among a well-characterized group of patients who have received successful HCC treatment interventions, relative to no DAA therapy?

Primary Objective	Primary Endpoint
Estimate the risk of early HCC recurrence (within the follow up period after the first HCC free image) associated with DAA therapy exposure relative to no DAA therapy exposure during routine clinical care of HCV-infected patients with successfully treated HCC, in the prospective DAA-PASS cohort.	Time to recurrence of HCC (from radiological confirmation of the absence of detectable disease following HCC treatment intervention) associated with DAA therapy exposure relative to no DAA therapy exposure in the prospective DAA-PASS cohort.

Secondary Objective	Secondary Endpoint
A. Compare the adjusted incidence of early HCC recurrence (within the follow up period after the first HCC free image) associated with DAA therapy exposure relative to no DAA therapy exposure during routine clinical care of HCV-infected patients with successfully treated HCC, in the prospective DAA-PASS cohort.	A. Number of events (early HCC recurrence) associated with DAA therapy exposure relative to no DAA therapy exposure, in the prospective DAA-PASS cohort.
B. Estimate the risk of early HCC recurrence (within the follow up period after the first HCC free image) associated with DAA therapy exposure relative to no DAA therapy exposure including a historical cohort of HCV patients not exposed to DAA with initial HCC diagnosis and subsequent successful treatment of HCC.	B. Time to recurrence of HCC (from radiological confirmation of the absence of detectable disease following HCC treatment intervention) associated with DAA therapy exposure from the prospective DAA-PASS cohort relative to no DAA therapy exposure including the historical cohort.
C. Compare the adjusted incidence of early HCC recurrence (within the follow up period after the first HCC free image) associated with DAA therapy exposure relative to no DAA therapy exposure including a historical cohort of HCV patients not exposed to DAA with initial HCC diagnosis and subsequent successful treatment of HCC.	C. Number of events (early HCC recurrence) associated with DAA therapy exposure from the prospective DAA-PASS cohort relative to no DAA therapy exposure including the historical cohort.
Exploratory Objective	
Describe in a non-comparative summary the cumulative risk of HCC recurrence over time for the historical cohort alone.	

4.4. Study Design

This prospective, observational study will estimate the risk of early HCC recurrence associated with DAA therapy exposure relative to no DAA therapy exposure during routine clinical care of HCV-infected patients with previous successfully treated HCC using a prospective cohort from TARGET-HCC.

DAA-PASS will include a prospective cohort and data from a historical cohort.

For the purposes of data analysis in DAA-PASS, the following definitions will be used:

- **Enrollment/Baseline:** the date of the **first HCC-free** (radiological) **image**
- **Successful treatment of HCC:** no evidence of enhancing liver lesions and no extrahepatic lesions consistent with new or persistent HCC on radiological imaging after HCC treatment intervention
- **First HCC-free image (Index Date):** the first radiological image that showed confirmation of **successful treatment of HCC**
- **Follow-up:** from Enrollment/Baseline up to 24 months

- **HCC recurrence:** evidence of enhancing liver lesions or extrahepatic lesions consistent with recurrence or new HCC on radiological imaging after **successful treatment of HCC**
- **Early HCC recurrence:** **HCC recurrence** within the follow up period after **the first HCC-free image**

Prospective Cohort

The prospective DAA-PASS cohort will include the following periods:

- Screening (participants identified in TARGET-HCC who fulfil the screening criteria)
- Enrollment/Baseline (participants with their first HCC-free image who fulfil the enrollment criteria)
- Follow-up (up to 24 months from Enrollment/Baseline)

During the follow-up period, which has a cutoff date of June 2021, participants will be managed per local standard of care which includes follow-up imaging according to guidelines established by the American Association for the Study of Liver Disease (AASLD) and the European Association for the Study of the Liver (EASL): AASLD Guidelines for the Treatment of Hepatocellular Carcinoma and EASL–European Organization for the Research and Treatment of Cancer (EORTC) Clinical Practice Guidelines: Management of Hepatocellular Carcinoma.

Upon completion of or early discontinuation from DAA-PASS, participants will continue to be followed in the TARGET-HCC study.

Historical Cohort

As part of Secondary Objectives B and C, data from the prospective DAA-PASS cohort will be integrated with data from a historical cohort of patients with active HCV infection who were successfully treated for previous HCC. The Italian Liver Cancer Group (ITA.LI.CA) study cohort has been identified as a source of historical cohort data for this analysis.

Additionally, a descriptive analysis for the Exploratory Objective will be performed to characterize the cumulative risk of HCC recurrence in the ITA.LI.CA study cohort only.

4.5. Population

Prospective Cohort

The prospective DAA-PASS cohort will include a subset of HCV RNA positive participants in the TARGET-HCC study who meet entry criteria including hepatitis C (with no prior history of DAA therapy) and newly diagnosed Barcelona Clinic Liver Cancer (BCLC) Stage A HCC. Participants will be enrolled in the countries participating in TARGET-HCC which will include the United States (US), France, Germany, Italy, and Spain.

Historical Cohort

The historical cohort will be derived from the ITA.LI.CA database, which includes data on all consecutive patients with HCC who were managed within participating centers in Italy. The historical cohort will include patients from the ITA.LI.CA database who have active HCV infection who were not treated for HCV (IFN-based or DAA-based regimens) during the follow-up period, with initial HCC diagnosis BCLC Stage A, and subsequent successful treatment of HCC with curative therapy.

4.6. Variables

The prospective DAA-PASS cohort will include information on participant demographics, laboratory values, medical history events, concomitant medication use (including hepatotoxic medications), alcohol use, staging of liver disease and HCC, HCC treatment intervention(s) and response, tumor assessments, additional liver imaging information, prior HCV treatment, and DAA therapy. Variables included in any models will be the last values collected from the time of initial HCC diagnosis through the first HCC-free image.

The historical cohort will include similar data extracted from the ITA.LI.CA database, as available.

4.7. Data Sources

Data for the prospective DAA-PASS cohort will be obtained through abstraction of the participant medical record into the TARGET-HCC database. For selected sites outside of the US, the abstraction will be performed by study site personnel (or designee) while for sites in the US, electronic copies of the participant information will be uploaded for abstraction or imported electronically. Imaging data will be abstracted from local radiological reports. Imaging information will be collected from initial HCC diagnosis through study follow-up (up to 24 months after the first HCC-free image).

Data for the historical cohort will come from the ITA.LI.CA database; data were abstracted from medical records at the time of initial HCC diagnosis and treatment; subsequent data abstractions were performed at the time of any HCC recurrence event.

4.8. Study Size

Initially a sample size of 600 enrolled participants was planned for the prospective DAA-PASS cohort to capture an expected 122 HCC recurrence events through the 24 months of follow-up based on a 15% annual recurrence rate or 195 expected HCC recurrence events based on a 25% annual recurrence rate. Due to enrollment challenges, convenience sample sizes between 40 and 70 participants are expected. Based on a meta-analysis from 3 US and European sites^{8,1}, the 1-year HCC recurrence rate is estimated as 35%. Thus, example confidence bounds using the 35% 1-year HCC recurrence rate follow. Assuming the DAA HR is equal to 1.0, a sample size of 70 participants with an HCC recurrence rate of 35% per 12 months will provide two-sided 95% confidence bounds of 0.46 to 2.82. Hence, the convenience sample size of 70 will distinguish from a HR of 3.0 if there is no additional HCC recurrence risk related to DAA exposure. A

sample size of 60 participants with an HCC recurrence rate of 35% per 12 months will provide two-sided 95% confidence bounds of 0.43 to 3.10, and no upper confidence bound is calculable with sample size less than or equal to 50 participants.

The historical cohort will include approximately 400 patients from the ITA.LI.CA database who have HCV and were diagnosed with HCC after 2007 (when the database began to capture follow-up clinical and imaging data), successfully treated for BCLC Stage A HCC with curative therapy, and not treated with DAAs for their HCV infection after HCC diagnosis.

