After 2 years of screening and enrollment in DAA-PASS, 30 participants have been enrolled. The primary reason for the low enrollment is that there are very few eligible patients. Most HCC patients are treated for HCV before they are treated for HCC. Assuming the DAA HR is equal to 1.0, a sample size of 70 participants with an HCC recurrence rate of 35% per 12 months will provide two-sided 95% confidence bounds of 0.46 to 2.82. Hence, a sample size of 70 can distinguish from a HR of 3.0 if there is no additional HCC recurrence risk related to DAA exposure. A sample size of 60 participants with an HCC recurrence rate of 35% per 12 months

will provide two-sided 95% confidence bounds of 0.43 to 3.10, and a sample size of 50 participants will yield two-sided 95% confidence bounds of 0.39 and infinity.

Historical Cohort

Information related to the analysis including historical cohort data is described in Section 9.7.9.

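### The upper part of the expected 40 to 70 participants, including the N=70 behind the hazard ratio 3.0 statement, is not supported by the protocol's own accrual

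*Protocol*

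**What the plan says.** Section 4.8, on the prospective cohort: "Due to enrollment challenges, convenience sample sizes between 40 and 70 participants are expected". No calculation leads to that range.

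At a 12-month recurrence rate of 35% and a true hazard ratio of 1.0, Sections 4.8 and 9.5.1 give these expected 95% bounds:

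- N=70: "will provide two-sided 95% confidence bounds of 0.46 to 2.82", from which 9.5.1 concludes that "a sample size of 70 can distinguish from a HR of 3.0". Section 4.8 draws the same conclusion.
- N=60: 0.43 to 3.10.
- N=50: 0.39 to infinity in 9.5.1. Section 4.8 says no upper bound can be calculated at 50 or fewer.

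On accrual, 9.5.1 reports: "After 2 years of screening and enrollment in DAA-PASS, 30 participants have been enrolled". Section 4.2 describes the trend after the 2019 remediation efforts: "overall the monthly screening and enrollment rates have decreased or have remained unchanged over the course of the year". It attributes this to a shortage of suitable patients, with the trend "likely reflecting the lack of the available eligible patient population". One of the remediation steps listed there is "identification of potential additional sites willing to consider participation within active countries".

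On timing, Section 4.4 reads: "During the follow-up period, which has a cutoff date of June 2021". The milestones put data collection from 1Q2018 to 2Q2021. Section 5 dates the two amendments concerned with sample size 24 March 2020 and 9 June 2020.

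Section 9.7.9 bases the precision of the pooled analysis on 50 prospective participants.

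**The concern.** The size section's one favourable conclusion, that a hazard ratio of 3.0 can be distinguished, holds only at 70, the top of the expected range. Reaching 70 means adding 40 participants to the 30 enrolled, in less time than the first 30 took, while the protocol describes a depleted pool and rates that are not rising.

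At stake is how the primary analysis is read. This is a regulator-requested safety study whose key criterion in 9.5.1 was to exclude a hazard ratio of 2.0. A reader who sees 3.0 offered as attainable within the expected range may not notice that, at the size accrual points to, the protocol's own figures give no finite upper bound. The pooled analysis, meanwhile, is sized on 50, so the two precision statements rest on different expectations for the same cohort.

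**Working it through.** **Inputs.** 30 enrolled in 24 months (9.5.1); cutoff June 2021 (4.4); amendment dates (5); start of data collection 1Q2018 (4.10 and 6). The range of 40 to 70 has no derivation in the protocol, so there is no figure to reproduce.

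**Months remaining.** The count of 30 is undated, so I use three values: 12 (from 9 June 2020), 15 (from 24 March 2020) and 18 (from the start of 2020, the earliest end of two years counted from 1Q2018).

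**Projection.** Rate = 30/24 = 1.25 per month, and N = 30 + 1.25 × months left.

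- 12 months: 30 + 15 = 45
- 15 months: 30 + 18.75 = 48.75
- 18 months: 30 + 22.5 = 52.5

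**Rate needed, as a multiple of 1.25 per month.**

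- For 60: 30/12 = 2.5 (2.0 times), 30/15 = 2.0 (1.6 times), 30/18 = 1.67 (1.33 times)
- For 70: 40/12 = 3.33 (2.67 times), 40/15 = 2.67 (2.13 times), 40/18 = 2.22 (1.78 times)

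**Prediction allowing for uncertainty in the rate.** Further enrollments follow a negative binomial with shape 30.5 and p = 24/(24 + months left).

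| Months left | 95% limits for N | P(N≥60) | P(N≥70) | P(N≤50) |
|---|---|---|---|---|
| 12 | 37 to 56 | 0.5% | below 0.1% | 86% |
| 15 | 39 to 61 | 4% | 0.1% | 63% |
| 18 | 42 to 66 | 15% | 1.0% | 38% |

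**Sensitivity to uneven accrual.** If a share s of the 30 came in the latest 12 months and that rate holds, N = 30 + (30s/12) × months left. For 12, 15 and 18 months:

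- s = 2/3: 50, 55, 60
- s = 0.8: 54, 60, 66
- s = 1: 60, 67.5, 75

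Of these, only the last case with 18 months left reaches 70.

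**Bounds.** I take the protocol's confidence bounds as stated. A rough simulation (time-dependent exposure, the uptake pattern in 9.5.1, full 24-month follow-up) came close to the bounds for 600. It gave narrower intervals at small sizes: about 0.4 to 2.5 at 70, and a finite upper bound of about 3 at 50. The protocol does not state its method, so nothing here rests on that check, but the bounds should be recalculated when the section is revised.

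**The case against.** The strongest reply is that the protocol contains no failed calculation. The projection of 45 to 52 lies inside 40 to 70, so a reader who infers that the whole range contradicts the accrual goes too far.

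Nor do the documents show that 60 and 70 cannot occur. The count of 30 is undated and its spread over the two years is not given. The flat or falling trend refers to 2019, not to the 24-month average, so an early slow start would put the 2019 rate above 1.25 per month. Extra sites were being sought. June 2021 is a follow-up cutoff, and no last enrollment date is stated. With 18 months left, even the inference that the final size is probably 50 or fewer fails, since that probability is then 38%.

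The weakness is also partly disclosed. The sentences after the N=70 statement give 3.10 at 60 and no upper bound at 50, the hazard ratio 3.0 conclusion is conditional on 70, and Section 9.7 makes the analyses contingent on the final size.

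All of this stands, and it limits the point to the upper part of the range. It does not rescue 70, which needs a strong acceleration that Section 4.2 reports did not happen. Letting accrual run to the cutoff is itself generous: the first follow-up image falls at 3 months (9.2.4), so anyone enrolled in the last 3 months has no scheduled post-baseline image by then. Disclosing the bounds at 50 and 60 also does not tell the reader which size to expect.

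**Conclusion.** The concern holds for the upper part of the range. The protocol's accrual projects to about 45 to 52 participants, with 95% predictive limits of about 37 to 66 across the three datings. N=70 has a probability of about 1% or less. N=60 is unlikely, at about 0.5% to 15%, but not excluded, and by the protocol's own figure it does not exclude 3.0. The central projection lies around 50, where the protocol gives no finite upper bound and which 9.7.9 already uses.

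This rests on uniform accrual at the two-year average, 12 to 18 months remaining, enrollment open to the cutoff, and no unusual screening backlog or gain from new sites. A falling rate would lower the projection, and a ramp-up before 2019 would raise it.

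A reader might conclude that the range should simply become 40 to 50 and that 60 should be dropped. That is too narrow: the same prediction puts only about 76%, 60% and 37% of its probability on 40 to 50 at 12, 15 and 18 months.

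**What to change.** In Sections 4.8 and 9.5.1:

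- Date the count of 30 and state an accrual-based expected size (about 45 to 52 on the figures now in the protocol), with its uncertainty and assumptions.
- Make the precision at about 50 the headline expectation for the primary objective, consistent with 9.7.9.
- Keep 60 as an optimistic scenario, with its upper bound of 3.10.
- Either give the accrual basis for 70, such as recent monthly enrollment, screening backlog or confirmed new sites, or label it not expected and withdraw the conclusion that the study will distinguish from a hazard ratio of 3.0.

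The cost is wording and recalculated bounds in two sections, with no additional participants. The downside is that the stated precision for the primary objective becomes less favourable.

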9.7.1. General Conventions

Descriptive statistical methods for interval-scale measures will include tabulation of count, mean, standard deviation, median, and range. For categorical measures with fixed levels the number of participants will be displayed along with percentages based on participants with available results.

Time to HCC recurrence will be summarized with a life table displaying the numbers of participants at risk entering the time interval, cumulative censored participants, and cumulative proportion with events at the end of the interval. HCC recurrence status will only be evaluated when imaging for HCC is completed. Methods designed to handle interval censoring will be utilized. In addition, if applicable, the cumulative number of participants ongoing or censored by time will be provided.

Descriptive summaries of baseline information, such as demographics, disease characteristics and HCC treatment interventions, will be tabulated. Populations of interest to be displayed in the descriptive summaries are outlined in Section 9.7.2.

All statistical estimates will be reported along with corresponding 95% two-sided CIs. P-values for model parameters will be provided based on Wald statistics.

Unless otherwise specified, all statistical computations will be performed using R software or SAS software (Version 9.4. Copyright © 2012, SAS Institute Inc., Cary, NC).

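### Sections 4.8 and 9.5.1 say no upper 95% bound exists at 50 or fewer participants; the plan's own inputs give a finite bound of roughly 3 to 4 at N=50

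*Protocol*

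**What the plan says.** Protocol section 4.8 replaces the original 600 participants with a smaller prospective cohort: "convenience sample sizes between 40 and 70 participants are expected". Precision is then shown for a true HR of 1.0 and 35% recurrence per 12 months:

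- N=70: "two-sided 95% confidence bounds of 0.46 to 2.82"
- N=60: 0.43 to 3.10
- N of 50 or less: "no upper confidence bound is calculable with sample size less than or equal to 50 participants"

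Section 9.5.1 repeats the first two and says of the third that "a sample size of 50 participants will yield two-sided 95% confidence bounds of 0.39 and infinity". Section 9.7.1 promises that "All statistical estimates will be reported along with corresponding 95% two-sided CIs". Section 9.7.9 takes 50 prospective participants as the planning size for the pooled analysis with about 400 historical patients.

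**The concern.** The three sample sizes share the same HR and recurrence rate. The lower bound moves smoothly (0.46, 0.43, 0.39), while the upper bound goes 2.82, 3.10, infinity. Removing ten of 60 participants should widen the interval by about a tenth on the log scale, not abolish one end of it.

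The affected range is not remote. It is the lower part of the stated 40 to 70 and includes the size used in section 9.7.9. For that range the protocol gives no usable expected precision for the primary HR from the prospective cohort alone. A reader could also take the sentence to mean that a study of this size cannot bound the HR at all.

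**Working it through.** **1. From the printed intervals alone.** The standard error of the log HR implied by an interval (L, U) is SE = ln(U/L) / (2 × 1.96).

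- N=70: ln(2.82/0.46) / 3.92 = 0.463
- N=60: ln(3.10/0.43) / 3.92 = 0.504
- Ratio 0.504/0.463 = 1.09, against √(70/60) = 1.08, so the two printed intervals follow ordinary scaling with √N.
- N=50: 0.463 × √(70/50) = 0.547 and 0.504 × √(60/50) = 0.552.
- With the printed lower bound of 0.39, U = 0.39 × exp(3.92 × SE) = 3.33 to 3.39, or about 3.4.

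**2. Inputs for a direct check.** From section 9.5.1: HR 1.0; 35% per 12 months, so a monthly hazard of −ln(0.65)/12 = 0.0359; DAA start in 42% by 6 months, a further 44% by 12 months and 4% between 12 and 24 months (taken as uniform within each window). From section 9.2.4: images at months 3, 6, 9, 12, 18 and 24.

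No censoring rate is given, so it was derived from the stated events at N=600. With recurrence hazard λ and censoring rate c, expected events = 600 × λ/(λ+c) × (1 − exp(−24(λ+c))). Setting this to 122 (15% per year, λ = 0.0135) or 195 (25% per year, λ = 0.0240) gives c = 0.029 per month both times, or about 0.35 per year. At N=50 and 35% this yields about 22 events (29 without censoring).

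**3. Reproducing the plan's figures.** These are mean 95% limits over simulated data sets that have a finite bound, from an unadjusted Cox model with time-dependent DAA exposure.

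| N, annual rate | Plan | Simulated mean |
|---|---|---|
| 600, 15% | 0.66–1.61 | 0.66–1.65 |
| 600, 25% | 0.72–1.39 | 0.70–1.44 |
| 70, 35% | 0.46–2.82 | 0.44–2.89 |
| 60, 35% | 0.43–3.10 | 0.41–3.20 |
| 50, 35% | 0.39–infinity | 0.38–3.74 |
| 40, 35% | not calculable | 0.34–4.82 |

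The finite printed bounds come out closely, and so does the lower bound at N=50. Only the upper bound at N=50 does not. Median limits are 0.33 to 2.97 at N=50 and 0.29 to 3.46 at N=40. A proportional hazards model on the imaging intervals, with exposure starting at the image before DAA start, gives means of 0.38 to 3.88 and 0.34 to 5.00, and medians of 0.33 to 2.97 and 0.29 to 3.38.

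**4. How often no finite bound exists.** This happens when one exposure state has no events.

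| Setting | N=50 | N=40 |
|---|---|---|
| Unadjusted, full 24 months (Cox / interval model) | 0.03% / 0.05% | 0.16% / 0.22% |
| June 2021 cutoff, uniform entry over 39 months (assumed) | about 0.2% | 0.8–1% |
| 11 further covariates, unrelated to outcome (assumed) | about 1% | about 4% |

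With the cutoff, events at N=50 fall to about 17, the mean upper bound rises to about 4.7 and the median to about 3.5. Further runs at N=50 gave no failure in 4,000 data sets without censoring, and 99.9% finite with early DAA start and doubled censoring.

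**The case against.** The best reply is that nothing hangs on the figure. The cohort is a convenience sample, and the ENCePP checklist (item 2.1.4) says the aim is estimation with confidence limits. No enrolment target, stopping rule or choice of analysis uses the bound for N of 50 or less, and the reported interval will come from the data. The error is also conservative: it overstates the imprecision. All of this stands and limits the weight of the point.

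It is also fair that section 9.7.9 does give finite bounds at exactly 50 prospective participants (0.51–2.13, 0.57–1.82 and 0.62–1.69 at 15%, 25% and 35%). Those serve Secondary Objective B, however, not the primary HR.

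One could defend the sentence by pointing to the planned model, which has ten covariates (one a random centre effect) on about 22 events. The plan does not give that as its reason, and 11 added covariates left about 99% of intervals finite at N=50 and 96% at N=40.

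Four stronger readings are tempting and not supported:

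- **Cause.** The printed intervals are off-centre (√(0.46 × 2.82) = 1.14; √(0.43 × 3.10) = 1.15). A reader might infer that simulated limits were averaged and one degenerate data set made the mean infinite. The protocol mentions no simulation. At 0.02–0.04% per data set, 1,000 replicates would contain such a set with a probability of only 18–33%. The cause stays open.
- **Most likely sample size.** Thirty participants in two years extrapolates to about 45 after a third, but the plan says only 40 to 70.
- **Dropping the primary interval.** Section 9.7 makes analyses contingent on sample size and events in general terms. It does not refer to this figure.
- **Interval method.** "P-values for model parameters will be provided based on Wald statistics" concerns P-values only. It does not fix how the confidence limits are computed, so it is no ground for requiring a penalised fit. That choice belongs in the SAP.

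**Conclusion.** The statements for N of 50 or less are wrong as written. The plan's own N=60 and N=70 intervals imply about 0.39 to 3.4 at N=50. Simulation at its inputs gives an upper bound of about 3.0 (median) to 3.7–3.9 (mean) at N=50, and 3.4–3.5 to 4.8–5.0 at N=40.

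The exact values rest on a censoring rate derived from the superseded 600-participant plan, full 24-month follow-up and an unadjusted model. Shorter follow-up or more covariates widen the bounds or raise the share of failures, but in no scenario run at 35% did that share exceed about 4%. A figure above 99.9% finite holds only at N=50 under the unadjusted, full-follow-up assumptions and should not be quoted for the whole range.

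This is a minor correction of a stated precision figure. It does not rescue the study's precision: at these sizes the expected interval would still not exclude an HR of 2.0, the criterion section 9.5.1 set for the original design, and on the mean summary it would not exclude 3.0 either.

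**What to change.** In sections 4.8 and 9.5.1:

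- Replace the statements on 50 or fewer participants with finite expected bounds for N=40, 45 and 50.
- Use one summary (median or geometric mean) for every N, including 60 and 70, so that the figures can be compared.
- State the censoring rate, the follow-up (with or without the June 2021 cutoff) and the model behind the bounds.
- Report the share of data sets without a finite bound as a separate number.
- Say plainly that at these sizes the interval is not expected to exclude an HR of 2.0.

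The cost is one precision calculation and a few edited sentences in two sections. It needs no new participants and no change to the analysis.
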